#### **6.5.5 Concomitant Medications**

The original terms recorded on the study subjects’ eCRF by the Investigator for concomitant medications will be standardized by the Sponsor by assigning preferred terms.

Concomitant medications will be presented in summary tables and listings.

### **6.6 PHARMACOKINETIC ANALYSES**

Non-compartmental analysis using WinNonlin software will be used to calculate PK parameters where appropriate. Summary descriptive statistics of plasma PK parameters, including  $C_{\max}$ ,  $T_{\max}$ ,  $AUC_{\text{inf}}$ ,  $AUC_{\text{last}}$ , and  $t_{1/2}$  for RO7062931 and any metabolites when available, will be presented by cohort including means, geometric means, standard deviations (SD), coefficients of variation (CV), medians and ranges. Note: the geometric mean and associated CV% will be used to describe  $C_{\max}$ ,  $AUC_{\text{inf}}$ ,  $AUC_{\text{last}}$ . Listings, summary tables and graphs (individual plots and/or mean plots) by treatment group will be provided. Descriptive statistics of urine PK parameters for RO7062931 and any metabolites will be presented, where available. PK data from this study may be pooled with data from other studies to develop a population PK model.

A high-contrast, black and white image showing a series of horizontal bars of varying lengths and positions. The bars are thick and appear to be composed of multiple pixels. The background is white, and the bars are black. The bars are arranged in a staggered, non-overlapping pattern across the frame.

## 6.7 OTHER ANALYSES

### 6.7.1 Liver and Kidney Biomarker Data

The kidney and liver biomarkers (see Section 4.6.1.8) will be explored graphically. Plots will include longitudinal plots for both actual result and change from baseline. Longitudinal plots will include individual subject responses by dose, as well as mean/median plots. Box and whisker plots may also be used to detect outliers.

## 6.8 INFLAMMATORY MARKERS, DRUG-INDUCED AUTOANTIBODIES AND ADA DATA

At minimum, any data that is collected as detailed in Section 4.6.1.7, and is available at the time of database closure will be listed and summarized using descriptive statistics. Data may also be explored graphically.

## 7. DATA COLLECTION AND MANAGEMENT

## 7.1 DATA QUALITY ASSURANCE

The Sponsor will be responsible for data management of this study, including quality checking of the data. Sites will be responsible for data entry into the EDC system.

A comprehensive validation check program will verify the data. Discrepancies will be generated automatically in the system at the point of entry or added manually for resolution by the Investigator.

The Sponsor will produce a Data Handling Manual and a Data Management Plan that describes the quality checking to be performed on the data. Central laboratory data and electronic data will be sent directly to the Sponsor, using the Sponsor's standard procedures to handle and process the electronic transfer of these data.

System backups for data stored by the Sponsor and records retention for the study data will be consistent with the Sponsor's standard procedures.

## **7.2 ELECTRONIC CASE REPORT FORMS**

Data for this study will be captured via an online EDC system. The data collected in the source documents is entered onto the study eCRF. An audit trail will maintain a record of initial entries and changes made; reasons for change; time and date of entry; and user name of person authorizing entry or change. For each HV enrolled, an eCRF must be completed and electronically signed by the principal Investigator or authorized delegate from the study staff. If a HV withdraws from the study, the reason must be noted on the eCRF. If a HV is withdrawn from the study because of a treatment-limiting adverse event, thorough efforts should be made to clearly document the outcome.

The Investigator should ensure the accuracy, completeness and timeliness of the data reported to the Sponsor/CRO in the eCRFs and in all required reports.

eCRFs will be submitted electronically to the Sponsor/CRO and should be handled in accordance with instructions from the Sponsor/CRO.

At the end of the study, the Investigator will receive subject data for his or her site in a readable format on a compact disc that must be kept with the study records.

Acknowledgement of receipt of the compact disc is required.

## **7.3 SOURCE DATA DOCUMENTATION**

Study monitors will perform ongoing source data verification to confirm that critical protocol data (i.e., source data) entered into the eCRFs by authorized site personnel are accurate, complete, and verifiable from source documents.

Source documents (paper or electronic) are those in which subjects' data are recorded and documented for the first time. They include, but are not limited to, hospital records, clinical and office charts, laboratory notes, memoranda, subject-reported outcomes, evaluation checklists, pharmacy dispensing records, recorded data from automated instruments, copies of transcriptions that are certified after verification as being accurate and complete, microfiche, photographic negatives, microfilm or magnetic media, X-rays,

subject files, and records kept at pharmacies, laboratories, and medico-technical departments involved in a clinical trial.

Before study initiation, data to be entered directly into the eCRFs (i.e., no prior written or electronic record of the data) and considered source data must be defined in the Trial Monitoring Plan.

Source documents that are required to verify the validity and completeness of data entered into the eCRFs must not be obliterated or destroyed and must be retained per the policy for retention of records described in Section 7.5.

To facilitate source data verification, the Investigators and institutions must provide the Sponsor direct access to applicable source documents and reports for trial-related monitoring, Sponsor audits, and IRB/EC review. The investigational site must also allow inspection by applicable health authorities.

#### **7.4 USE OF COMPUTERIZED SYSTEMS**

When clinical observations are entered directly into an investigational site's computerized medical record system (i.e., in lieu of original hardcopy records), the electronic record can serve as the source document if the system has been validated in accordance with health authority requirements pertaining to computerized systems used in clinical research. An acceptable computerized data collection system allows preservation of the original entry of data. If original data are modified, the system should maintain a viewable audit trail that shows the original data as well as the reason for the change, name of the person making the change, and date of the change.

#### **7.5 RETENTION OF RECORDS**

Records and documents pertaining to the conduct of this study and the distribution of IMP, including eCRFs, Informed Consent Forms, laboratory test results, and medication inventory records, must be retained by the Principal Investigator for at least 15 years after completion or discontinuation of the study, or for the length of time required by relevant national or local health authorities, whichever is longer. After that period of time, the documents may be destroyed, subject to local regulations. No records may be disposed of without the written approval of the Sponsor. Written notification should be provided to the Sponsor prior to transferring any records to another party or moving them to another location.

### **8. ETHICAL CONSIDERATIONS**

#### **8.1 COMPLIANCE WITH LAWS AND REGULATIONS**

This study will be conducted in full conformance with the ICH E6 guideline for Good Clinical Practice and the principles of the Declaration of Helsinki, or the laws and regulations of the country in which the research is conducted, whichever affords the greater protection to the individual. The study will comply with the requirements of the

ICH E2A guideline (Clinical Safety Data Management: Definitions and Standards for Expedited Reporting). Studies conducted in the United States or under a U.S. Investigational New Drug (IND) application will comply with U.S. FDA regulations and applicable local, state, and federal laws. Studies conducted in the EU/EEA will comply with the EU Clinical Trial Directive (2001/20/EC).

## **8.2 INFORMED CONSENT**

The Sponsor's sample Informed Consent Form (and ancillary sample Informed Consent Forms such as a Child's Assent or Caregiver's Informed Consent Form, if applicable) will be provided to each site. If applicable, it will be provided in a certified translation of the local language. The Sponsor or its designee must review and approve any proposed deviations from the Sponsor's sample Informed Consent Forms or any alternate consent forms proposed by the site (collectively, the "Consent Forms") before IRB/EC submission. The final IRB/EC-approved Consent Forms must be provided to the Sponsor for health authority submission purposes according to local requirements.

The Consent Forms must be signed and dated by the subject before his or her participation in the study. The case history or clinical records for each patient shall document the informed consent process and that written informed consent was obtained prior to participation in the study.

The Consent Forms should be revised whenever there are changes to study procedures or when new information becomes available that may affect the willingness of the subject to participate. The final revised IRB/EC-approved Consent Forms must be provided to the Sponsor for health authority submission purposes.

Subjects must be re-consented to the most current version of the Consent Forms (or to a significant new information/findings addendum in accordance with applicable laws and IRB/EC policy) during their participation in the study. For any updated or revised Consent Forms, the case history or clinical records for each subject shall document the informed consent process and that written informed consent was obtained using the updated/revised Consent Forms for continued participation in the study.

A copy of each signed Consent Form must be provided to the subject. All signed and dated Consent Forms must remain in each subject's study file or in the site file and must be available for verification by study monitors at any time.

## **8.3 INSTITUTIONAL REVIEW BOARD OR ETHICS COMMITTEE**

This protocol, the Informed Consent Forms, any information to be given to the subject, and relevant supporting information must be submitted to the IRB/EC by the Principal Investigator and reviewed and approved by the IRB/EC before the study is initiated. In addition, any subject recruitment materials must be approved by the IRB/EC.

The Principal Investigator is responsible for providing written summaries of the status of the study to the IRB/EC annually or more frequently in accordance with the requirements, policies, and procedures established by the IRB/EC. Investigators are also responsible for promptly informing the IRB/EC of any protocol amendments (see Section 9.5).

In addition to the requirements for reporting all adverse events to the Sponsor, investigators must comply with requirements for reporting serious adverse events to the local health authority and IRB/EC. Investigators may receive safety reports or other safety-related communications from the Sponsor. Investigators are responsible for ensuring that such reports are reviewed and processed in accordance with health authority requirements and the policies and procedures established by their IRB/EC, and archived in the site's study file.

#### **8.4 CONFIDENTIALITY**

The Sponsor maintains confidentiality standards by coding each patient enrolled in the study through assignment of a unique patient identification number. This means that subject names are not included in data sets that are transmitted to any Sponsor location.

Subject medical information obtained by this study is confidential and may only be disclosed to third parties as permitted by the Informed Consent Form (or separate authorization for use and disclosure of personal health information) signed by the patient, unless permitted or required by law.

Medical information may be given to a subject's personal physician or other appropriate medical personnel responsible for the subject's welfare, for treatment purposes.

Data generated by this study must be available for inspection upon request by representatives of the U.S. FDA and other national and local Health Authorities, Sponsor monitors, representatives, and collaborators, and the IRB/EC for each study site, as appropriate.

#### **8.5 FINANCIAL DISCLOSURE**

Investigators will provide the Sponsor with sufficient, accurate financial information in accordance with local regulations to allow the Sponsor to submit complete and accurate financial certification or disclosure statements to the appropriate health authorities. Investigators are responsible for providing information on financial interests during the course of the study and for one year after completion of the study (i.e., LSLO).

### **9. STUDY DOCUMENTATION, MONITORING, AND ADMINISTRATION**

#### **9.1 STUDY DOCUMENTATION**

The Investigator must maintain adequate and accurate records to enable the conduct of the study to be fully documented, including but not limited to the protocol, protocol

amendments, Informed Consent Forms, and documentation of IRB/EC and governmental approval. In addition, at the end of the study, the Investigator will receive the subject data, which includes an audit trail containing a complete record of all changes to data.

## **9.2 SITE INSPECTIONS**

Site visits will be conducted by the Sponsor or an authorized representative for inspection of study data, subject' medical records, and eCRFs. The Investigator will permit national and local health authorities, Sponsor monitors, representatives, and collaborators, and the IRBs/ECs to inspect facilities and records relevant to this study.

## **9.3 ADMINISTRATIVE STRUCTURE**

The Sponsor of the trial is F. Hoffmann-La Roche Ltd. The Sponsor is responsible for the study management, data management, statistical analysis and medical writing for the clinical study report.

The Sponsor is also responsible for managing CROs and central laboratories used in the study.

## **9.4 PUBLICATION OF DATA AND PROTECTION OF TRADE SECRETS**

The results of this study may be published or presented at scientific meetings. If this is foreseen, the Investigator agrees to submit all manuscripts or abstracts to the Sponsor prior to submission. This allows the Sponsor to protect proprietary information and to provide comments based on information from other studies that may not yet be available to the Investigator.

The Sponsor will comply with the requirements for publication of study results. In accordance with standard editorial and ethical practice, the Sponsor will generally support publication of multicenter trials only in their entirety and not as individual center data. In this case, a coordinating Investigator will be designated by mutual agreement.

Any formal publication of the study in which contribution of Sponsor personnel exceeded that of conventional monitoring will be considered as a joint publication by the Investigator and the appropriate Sponsor personnel.

Authorship will be determined by mutual agreement and in line with International Committee of Medical Journal Editors authorship requirements.

Any inventions and resulting patents, improvements, and/or know-how originating from the use of data from this study will become and remain the exclusive and unburdened property of the Sponsor, except where agreed otherwise.

## **9.5            PROTOCOL AMENDMENTS**

Any substantial protocol amendments will be prepared by the Sponsor. Substantial protocol amendments will be submitted to the IRB/EC and to regulatory authorities in accordance with local regulatory requirements.

Approval must be obtained from the IRB/EC and regulatory authorities (as locally required) before implementation of any changes, except for changes necessary to eliminate an immediate hazard to patients or any non-substantial changes, as defined by regulatory requirements.

## Appendix 1 Schedule of Assessments – Main table

Protocol Activity	Screening	Period 1								Follow Up		
Scheduled Time	Day -28 to -2	Day -1	Day 1	Day 2	Day 3	Day 4	Day 5	Day 6	Day 8	Day 15	Day 29	Day 85 e
Visit Window										(± 1 day)	(± 2 days)	(± 7 days)
Informed Consent	X											
Inclusion + Exclusion Criteria	X	X										
Demography	X											
Medical History	X											
Physical Examination h	X	X								X	X	X
Vital Signs	X	X	5	X	X	X	X	X	X	X	X	X
ECG-12 lead	X	X	5	X						X	X	X
Hematology a	X	X		X						X	X	X
Blood Chemistry a	X	X		X						X	X	X
Urinalysis a	X	X		X						X	X	X
Serology	X											
Coagulation a	X	X		X						X	X	X
Inflammatory markers g			3	X						X		
Drug-induced antibodies i				X d						X	X	X
ADA f				X d						X	X	X
Urine kidney biomarkers				X d	X	X				X	X	X
Blood liver biomarkers		X		X						X	X	X
Pregnancy Test b	X	X										X
FSH c	X											
Substance Use	X	X										
Admission		X										
Discharge					X							
Ambulatory Visit	X						X	X	X	X	X	X
Randomisation		X	X									
Medication			X									
Blood PK Sample a			12	3	X	X	X	X	X			
Urine PK Sample j			4	X								
Adverse Events	X	X	X	X	X	X	X	X	X	X	X	X
Treatments	X	X	X	X	X	X	X	X	X	X	X	X

## **Appendix 1 Schedule of Assessments – Main table (cont.)**

- a) Timing of PK sampling may change based on PK results from the FIH (BP39405) study, blood sample for PK and safety laboratory assessments will be collected in the event of a SAE or at early termination.
- b) Blood for beta-human chorionic gonadotropin ( $\beta$ -HCG) for pregnancy test at Screening, urine on all other occasions.
- c) FSH only for females and to confirm post-menopausal.
- d) Pre-dose.
- e) If necessary, subjects may be asked to return for additional follow-up visits.
- f) For ADA samples will be stored and will only be analyzed in case an immune driven AE/AE suggestive of inflammatory involvement occurs or in case of an atypical PK result.
- g) In case an immune driven AE/AE suggestive of immunological involvement occurs, an unscheduled sample will be collected and analyzed.
- h) Complete physical examination, is required at Screening and Day – 1. At all other visits (or as clinically indicated), limited, symptom-directed physical examinations should be performed at the discretion of the Investigator.
- i) In case an autoimmune driven AE/AE suggestive of autoimmunological involvement occurs, an unscheduled sample will be collected and analysed.
- j) Urine collection periods [0-4], [4-8], [8-12] and [12-24] hours post-dose.

## Appendix 2 Schedule of Assessments – Detailed table

Period	Day	Scheduled Time (h)	Administration of Study Medication	Vital Signs	ECG-12 lead	Inflammatory markers	Drug-induced antibodies	ADA	Urine kidney biomarkers	Blood liver biomarkers	Blood PK Sample	Urine PK Sample a
Screening	Day -28 to -2			X	X							
	Day -1			X	X					X		
Period 1	Day 1	Predose		X	X	X	X	X	X		X	
		0	X									X
		0.25										X
		0.5										X
		1		X	X						X	
		1.5									X	
		2									X	
		3				X					X	
		4		X	X						X	X
		6									X	
		8		X	X						X	X
		12		X	X	X					X	X
		18										X
	Day 2	24		X	X	X			X	X	X	X
		30										X
		36										X
	Day 3	48		X					X		X	
	Day 4	72		X							X	
	Day 5	96		X							X	
	Day 6	120		X							X	
	Day 8	168		X	X	X			X	X	X	
Follow up Visit	Day 15 (± 1 day)			X	X		X	X		X		
	Day 29 (± 2 days)			X	X		X	X	X	X		
	Day 85 (± 7 days)			X	X		X	X	X	X		

a) Urine collection periods [0-4], [4-8], [8-12] and [12-24] hours post-dose.

## Appendix 3

### Alcohol Unit Calculation - Examples

From Australian Department of Health (Population Health Division)

<http://www.alcohol.gov.au/internet/alcohol/publishing.nsf/Content/standard>

## Appendix 3

### Alcohol Unit Calculation - Examples (cont.)

These are only an approximate number of standard drinks. Always read the container for the exact number of standard drinks.

These are only an approximate number of standard drinks. Always read the container for the exact number of standard drinks.

\* Ready-to-Drink

**Appendix 4**  
**Toxicity Table for Grading Injection Reactions**

Parameter	Grade 1	Grade 2	Grade 3
Pain	Mild tenderness at injection site	Moderate pain without limitation of usual activities	Severe pain requiring prescription non topical analgesics or limiting usual activities
Erythema average diameter (mm) of skin redness at the site of injection	Present but < 25mm	<math>\geq 25</math> mm but < 50 mm	<math>\geq 50</math> mm
Swelling, (same grading as erythema)	Present but < 25mm	<math>\geq 25</math> mm but < 50 mm	<math>\geq 50</math> mm
Pruritus	Mild, not requiring any treatment	Requiring topical treatment	Refractory to topical treatment, OR requiring oral or parenteral treatment

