### **5.1.3        Non-Serious Adverse Events of Special Interest (Immediately Reportable to the Sponsor)**

Non-serious adverse events of special interest are required to be reported by the Investigator to the Sponsor immediately (i.e., no more than 24 hours after learning of the event; see Section [5.4.2](#) for reporting instructions). Adverse events of special interest for this study include the following:

- Cases of an elevated ALT or AST in combination with either an elevated bilirubin or clinical jaundice, as defined in Section [5.3.5.6](#).
- Suspected transmission of an infectious agent by the study drug, as defined below:  
Any organism, virus, or infectious particle (e.g., prion protein transmitting transmissible spongiform encephalopathy), pathogenic or non-pathogenic, is considered an infectious agent. A transmission of an infectious agent may be

suspected from clinical symptoms or laboratory findings that indicate an infection in a subject exposed to a medicinal product. This term applies only when a contamination of the study drug is suspected.

- Severe injection site reactions.
- Renal adverse events defined as serum creatinine  $1.5 \times$  upper limit of normal (ULN) or increase of  $\geq 50\%$  from baseline.

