## **5.3 METHODS AND TIMING FOR CAPTURING AND ASSESSING SAFETY PARAMETERS**

The Investigator is responsible for ensuring that all adverse events (see Section 5.1 for definition) are recorded on the Adverse Event eCRF and reported to the Sponsor in accordance with instructions provided in this section and in Sections 5.4-5.6.

For each adverse event recorded on the Adverse Event eCRF, the Investigator will make an assessment of seriousness (see Section 5.1.2 for seriousness criteria), severity (see Section 5.3.3), and causality (see Section 5.3.4).

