#### **Table 1   Adverse Event Severity Grading Scale**

Severity	Description
Mild	Discomfort noticed, but no disruption of normal daily activity
Moderate	Discomfort sufficient to reduce or affect normal daily activity
Severe	Incapacitating with inability to work or to perform normal daily activity

Note: Regardless of severity, some events may also meet seriousness criteria. Refer to definition of a serious adverse event (see Section 5.1.2).

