#### **5.3.5.1 Diagnosis versus Signs and Symptoms Injection-Site Reactions**

Adverse events that occur during or after study drug administration and are judged to be related to the SC study drug injection should be captured as a diagnosis (e.g., "injection reaction" on the Adverse Event eCRF. If possible, avoid ambiguous terms (such as "systemic reaction"). Associated signs and symptoms should be recorded on the dedicated Injection Reaction eCRF. *Grading of pre-defined injection site reaction symptoms is described in [Appendix 4](#).* If a subject experiences both a local and systemic reaction to the same dose of study drug, each reaction should be recorded separately on the Adverse Event eCRF, with signs and symptoms also recorded separately on the dedicated Injection Reaction eCRF.

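### Does it matter that Section 5.1.3 does not say which scale makes an injection-site reaction severe?

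*Combined protocol and SAP*

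**What the plan says.** Section 5.1.3 lists four kinds of non-serious event that the investigator must report within 24 hours. One is given only as "Severe injection site reactions". The liver item points to Section 5.3.5.6, the infectious-agent item is defined in the text beneath it, and the renal item has numeric creatinine limits.

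Section 5.3.3 offers Table 1 as the guide to adverse event severity in the study. Its top category, Severe, is worded "Incapacitating with inability to work or to perform normal daily activity". One step down, the Moderate category is worded "Discomfort sufficient to reduce or affect normal daily activity", and the lowest category, Mild, is worded "Discomfort noticed, but no disruption of normal daily activity".

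Section 5.3 requires a Section 5.3.3 severity for each entry on the Adverse Event eCRF. Section 5.3.5.1 puts an injection reaction on that form as a diagnosis and sends its signs and symptoms to a separate Injection Reaction eCRF. It then adds: "Grading of pre-defined injection site reaction symptoms is described in" Appendix 4.

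Appendix 4 grades pain, erythema, swelling and pruritus from 1 to 3. Pain Grade 2 is "Moderate pain without limitation of usual activities" and pain Grade 3 is "Severe pain requiring prescription non topical analgesics or limiting usual activities".

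**The concern.** The two scales place the effect on activity at different levels. In Appendix 4, limitation of activity belongs to Grade 3, the cell that also uses the word *severe*. In Table 1, reduced activity is Moderate, and Severe needs incapacity. Section 5.1.3 uses the word *severe* and cites neither scale. Section 5.1.2 adds to the doubt, because it allows severity to be rated either as mild, moderate or severe or by pre-defined criteria.

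Two investigators could therefore see the same painful reaction and differ on whether the 24-hour clock has started. Special-interest events are named in the first safety outcome (Section 3.3.1), and the sponsor evaluates them promptly for new findings (Section 5.7). With 8 active subjects per cohort, one event classified differently moves a cohort's special-interest proportion by 1/8 = 12.5 percentage points.

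**Working it through.** The plan gives no figure to reproduce and no injection-reaction rate, so the check sets the two scales side by side and then follows the consequence through the plan.

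**Step 1: where the scales can disagree about *severe*.** Appendix 4 has 4 signs × 3 grades = 12 cells. For pain:

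| Pain | Appendix 4 | Table 1 | Can the Section 5.1.3 trigger differ? |
|---|---|---|---|
| Mild tenderness, activity undisturbed | Grade 1 | Mild | No |
| Moderate pain, activity not limited | Grade 2 | Mild, or Moderate if activity is affected without being limited | No |
| Severe pain needing a prescription non-topical analgesic, activity not prevented | Grade 3 | Mild or Moderate, by effect on activity | Yes |
| Severe pain, activity limited but not prevented | Grade 3 | Moderate | Yes |
| Incapacitating pain | Grade 3 | Severe | No |

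The two rows marked Yes are the same Appendix 4 cell, reached by its two alternative conditions. The Grade 2 row may or may not carry different labels on the two scales, but neither label is *severe*, so it cannot affect 24-hour reporting.

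The other 4 − 1 = 3 Grade 3 cells (erythema, swelling, pruritus) do not use the word *severe* and have no activity criterion. They would alter the trigger only if Grade 3 were equated with severe, and no passage does that. The direct conflict is therefore 1 cell of 12.

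On a strict reading of that cell, the pain must already be judged severe before either condition applies. Limiting pain that is not severe would then have no grade at all. That would be a gap inside Appendix 4, and the pain would not be called severe on either scale.

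**Step 2: which scale the text supplies by default.** Section 5.1.3 lists adverse events. An injection reaction is an Adverse Event eCRF entry (Section 5.3.5.1), every such entry takes a Section 5.3.3 severity (Section 5.3), and Section 5.3.3 offers only Table 1, where Severe is a named category. Appendix 4 uses numbered grades, is invoked only for symptoms, and feeds a different form. The natural reading is one scale for the event and another for its symptoms.

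**Step 3: what depends on the answer.**

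- *Data capture.* The diagnosis with its Table 1 severity and the graded symptoms are both recorded whichever scale triggers the 24-hour report. An analyst can count reactions either way.
- *Safety summaries.* Section 6.5 lists and summarises injection-site reactions by treatment and dose level, with placebo pooled. Section 6.5.1 plans listings and frequency tables by body system, with no separate analysis of the special-interest count.
- *Dose escalation.* Section 3.1.3 names Table 1 for severity at the review teleconferences. The criterion in Section 3.1.2.2 (more than 2 of 8 active subjects) also counts events the investigator finds clinically significant, so a limiting pain reaction is not shut out by a Moderate label.
- *Sponsor awareness.* Under Section 3.1.3 the investigator reports each subject's status after dosing and contacts the sponsor at once about any safety concern. Medically significant events are serious under Section 5.1.2 and carry their own 24-hour requirement.

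**The case for a change.** The best case for a change is that this is the only one of the four special-interest items with no definition, although it starts a 24-hour clock. Appendix 4 and its link in Section 5.3.5.1 came in with Version 2, and the current Section 5.1.3 has no matching link. Appendix 4 is the scale written for injection reactions, so an investigator could reasonably take it as the specific rule, and Section 5.1.2 leaves room for that. If Table 1 governs instead, pain called severe on one form is Moderate on the other, and nothing explains the difference.

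Part of this stands. The cross-reference is missing, the pain row and Table 1 do not agree on activity, and investigators could differ on when to report that kind of pain. The 12.5-point shift is correct arithmetic for one event in 8 subjects. It applies to a count that has no pre-specified analysis and no decision threshold, and it assumes such an event occurs.

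The argument that Appendix 4 must govern goes too far. Only one of its four Grade 3 cells mentions severity, so it cannot define a severe erythema, swelling or pruritus reaction without an added rule.

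**Conclusion.** No change to the plan follows. The gap is a missing cross-reference plus one Appendix 4 cell whose wording differs from Table 1. Its reach is possible inconsistency in the 24-hour reporting of severe pain that is not incapacitating. Recorded data, planned safety summaries and escalation review are the same under either reading.

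This rests on two assumptions: that sites complete both forms as Section 5.3.5.1 requires, and that Table 1 is used for event severity as Sections 5.3 and 5.3.3 direct. The likely frequency cannot be given, because the documents state no reaction rate.

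The sponsor can reconcile the two wordings in form-completion guidance. Which threshold should govern is the sponsor's decision, and no view is taken here.
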